- All participating centres are required to register the study according to local regulations. Evidence of successful registration must be uploaded onto REDCap prior to commencement of data collection. Centres will not be allowed to upload patients' data onto REDCap without evidence of successful registration of the study.
- In the UK, COMPASS has been designated an audit of practice. Internationally, individual study investigators are responsible for ensuring the correct audit, ethical or departmental approval has been achieved prior to commencing data collection (this can be registered as an audit or service evaluation, if appropriate).
- Following the conclusion of the study, it is recommended that mini-teams at each centre present the study findings to their hospital's surgery departments as part of the audit process.

Providing feedback on the project's findings to your department's clinicians is an essential step for improving care. Presenting local results will help you to develop your presentation skills & CV.

6. Eligibility criteria

Summary: Consecutive adult patients (≥ 18 years of age) undergoing emergency or elective colorectal surgery through any operative approach should be included.

- **Inclusion criteria**

Age	Age 18 years or above.
Procedure	Any formation of colostomy/ileostomy, resection of large bowel, or reversal of stoma (See Appendix B for full list).
Urgency	Emergency and elective procedures.
Technique	Open, laparoscopic, laparoscopic converted, robotic, robotic converted procedures are all eligible.

- **Exclusion criteria**

Procedures	
 • Appendicectomy (unless procedure involves a right hemicolectomy) • Transanal surgery - e.g. TaTME, TEMS, TAMIS, Altemeier's procedure. • Primarily urological procedure - e.g. ileal conduit. • Primarily gynaecological procedure - e.g. Hartmann's during ovarian cancer surgery • Primarily vascular procedure - e.g. bowel resection during AAA repair. • Diagnostic laparoscopy or laparotomy without resection of colon or rectum • Inguinal, incisional or femoral hernia, without resection of colon or rectum • Surgery involving major multi-visceral surgery – e.g. pelvic exenteration
Re-operation	Each individual patient should only be included in the COMPASS study once. Return to theatre during the same admission or follow up is regarded as a complication .

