▲ If an in-hospital patient recovering from another primary procedure NOT previously included undergoes emergency surgery, this **MUST** be included in the study as emergency case. ▲

i.e. Patient A is recovering from an AAA repair and undergoes large bowel resection due to bowel ischaemia one day later the previous surgery. He was correctly not included after the AAA repair, as that is a primarily vascular procedure and it did not involve any large bowel resection, but should be included after the bowel resection.

- ▲ You should collect data on consecutive elective patients operated at your hospital during the data collection period. **All eligible patients** must be included. Strategies to identify consecutive patients could include: ▲
- Daily review of elective theatre lists.
 - Daily review of handover sheets and ward lists.
 - Daily review of theatre logbooks
 - Daily on call review of patients undergoing emergency surgery

7. Outcome Measures

I. Primary outcome measure:

- Adherence to selected Enhanced Recovery After Surgery (ERAS) guidelines regarding rate of routine prophylactic drain insertion in colorectal surgery (22).

II. Secondary outcome measures:

- Rate of intra-abdominal postoperative collections, defined as collections which alter the normal postoperative course (e.g. requiring either medical, radiological, endoscopic or surgical intervention) (23).
- Time-to-diagnosis (days) of intra-abdominal postoperative collections defined as collections which alter the normal postoperative course (e.g. requiring either medical, radiological, endoscopic or surgical intervention) (23).
- Rate of drain-related complications defined as:
 - Surgical site infection (Centers for Disease Control and Prevention – CDC – definition: A surgical site infection is an infection that occurs after surgery in the part of the body where the surgery took place);
 - Cutaneous irritation at the drain insertion site (defined as reversible damage of the skin associated with rash, dry skin, itchiness, red discolouration and/or hives);
 - Small bowel evisceration and herniation of omentum (defined as prolapse of small bowel and/or omentum through the drain site after the removal of the drain);
 - Bowel injury (defined as intraoperative identification of or CT-proven drain-related iatrogenic bowel perforation) (7,24).

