Appendix C: Clavien-Dindo classification system

Adverse post-operative events may be divided up into treatment failures, sequelae and complications.

- **Failure of treatment** occurs when the original surgery fails to achieve its intended benefits; for example, persistent pain following laparoscopic cholecystectomy or tumour recurrence following cancer surgery.
- **Sequelae** are the recognised consequences of a given procedure; for example, gut malabsorption following a large small bowel resection or immune deficiency following splenectomy.
- **Complication:** Any deviation from the normal post-operative course that has an adverse effect on the patient and is not either a treatment failure or sequel.

In the Clavien-Dindo classification (13), the factor determining the severity of a complication is the treatment required. Consequently, a given complication may be graded differently depending on how it has been managed. For example, an anastomotic leak may be managed just with antibiotics if it is contained (grade II) or it may require re-operation under anaesthetic (grade III).

Some other considerations:

Intra-operative complications are not considered unless they have an adverse effect on the patient post-operatively. The only exception to this is **intra-operative death**; this is classified as grade V.

All post-operative adverse events are included, even when there is no direct relationship to the surgery.

All adverse events within the follow-up period (30 days) are included, even if they occur following discharge.

Diagnostic procedures are not included. For example, a diagnostic oesophagoduodenoscopy (OGD) to look for a source of bleeding without any intervention would not be considered a complication, but a therapeutic OGD with clipping of a bleeding vessel would be considered a grade III complication. Since **negative exploratory laparotomies** are considered to be diagnostic procedures, they should not be recorded as complications.

Grade	Definition (examples listed in italics)

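### The boxed inclusion rule in Section 6 also captures returns to theatre after an eligible operation done before the data collection window, which the Re-operation row counts as complications

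*Protocol*

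**What the plan says.** Three rules in the protocol bear on this.

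- **Re-operation row** (Section 6, exclusion table): "Each individual patient should only be included in the COMPASS study once". It continues: "Return to theatre during the same admission or follow up is regarded as a" complication. The second sentence is not expressly limited to patients already in the study.
- **Boxed note** (Section 6, after the table): "If an in-hospital patient recovering from another primary procedure NOT previously included undergoes emergency surgery", the emergency operation must be entered. The example is a large bowel resection for ischaemia the day after an aortic aneurysm repair, and the reason given is: "He was correctly not included after the AAA repair, as that is a primarily vascular procedure and it did not involve any large bowel resection".
- **Time window** (Section 4): a patient is included if knife-to-skin time falls inside one of the 14-day periods.

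Appendix B lists stoma formation and the colonic and rectal resections as eligible procedures, and Section 6 admits "Emergency and elective procedures". Section 7 defines POD 0 as the day of surgery, and Section 10 counts secondary outcomes from Day 0 to Day 30.

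**The concern.** The box turns on whether the first operation was included, not on whether it was eligible. An eligible colorectal operation done a few days before the window was not included, purely because of its date. If that patient, still in hospital, returns to theatre inside the window for a leak or collection and has a stoma formed or bowel resected, the box makes the return a compulsory index case. The Re-operation row, read as it stands, makes the same event a complication. Two mini-teams could code identical patients in opposite ways.

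Patients entered this way may already have the collection or leak when their study clock starts, and that clock starts at the re-operation rather than the original surgery. They are also likely to be drained. A secondary aim in Section 3 asks whether a drain is associated with earlier detection of collections and leaks. Adding drained patients whose collection predates POD 0 pushes that comparison towards earlier detection with a drain, and raises the collection rate.

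**Working it through.** **Text check.** Take one patient: an anterior resection two days before the window opens, then an emergency return on day 4 of the window, same admission, for a leak, with stoma formation.

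- Section 4: the first operation is outside the window, so it is not included.
- Section 6 box: emergency surgery in an in-patient whose first procedure was not included, so it must be entered.
- Section 6 Re-operation row: a return to theatre in the same admission, so it is a complication.
- Appendix A: the only field on earlier surgery is a yes/no history of abdominal surgery, which does not single out a same-admission re-operation. Section 9 describes Appendix A as the full list of required fields.

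In the aneurysm example the rules agree: the first operation was ineligible, there is no study record to hold a complication, and the patient enters once.

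**Size.** The protocol states no figure for this, so all rates below are assumptions.

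- r, re-operation rate: 3% to 10%
- d, mean delay to re-operation: 4 to 10 days
- e, share of re-operations that are an eligible procedure: 30% to 100%
- q, drain rate in these cases: 70% to 100%
- background drain rate: 35%. The Study Background gives this as a share of centres that drain most patients, not of patients, so it is only illustrative.

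With steady activity, a fraction d/14 of re-operations in a 14-day window follow an operation done before it. Extra index cases per regular case: x = r × (d/14) × e. Share of cohort: s = x/(1 + x). Shift in a crude any-drain rate: s × (q − 0.35).

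- Low: x = 0.03 × 4/14 × 0.3 = 0.0026; s = 0.26%, or 13 of 5000; shift at q = 70%: 0.09 points.
- Middle: x = 0.06 × 7/14 × 0.7 = 0.021; s = 2.06%, or 103 of 5000; shift 0.72 (q = 70%) to 1.34 points (q = 100%).
- High: x = 0.10 × 10/14 × 1.0 = 0.0714; s = 6.67%, or 333 of 5000; shift at q = 100%: 4.33 points.

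**Effect on collections.** Further assumptions: 90% of these cases drained and 40% with a collection; in all others 35% drained and 6% with a collection, independent of drainage.

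- The collection rate rises by s × (0.40 − 0.06): 0.1, 0.7 and 2.3 points in the low, middle and high cases.
- Middle case, drained patients: 103 × 0.9 × 0.4 = 37 collections from these cases, against 4897 × 0.35 × 0.06 = 103 from the rest. Their share is 37/140 = 26%.
- Middle case, undrained patients: 103 × 0.1 × 0.4 = 4, against 4897 × 0.65 × 0.06 = 191. Their share is 4/195 = 2%.
- By the same sums, the shares in drained and undrained patients are 4% and 0.3% in the low case, and 55% and 7% in the high case.

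**Why these are upper figures.** 300 centres × 3 per week × 2 weeks gives 1800 patients per period, so 5000 needs about 2.8 periods per centre. Periods 1 and 2, and periods 2 and 3, are seven days apart. If delay were uniform over days 1 to 14, the fraction of pre-window cases whose first operation was more than seven days before the window is (1 + 2 + … + 7)/(1 + 2 + … + 14) = 28/105 = 27%. At a centre that ran both periods, these patients were already included and the once-only rule bars re-entry.

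**The case against.** The strongest defence is that the box and the Re-operation row address different patients. The row opens with the once-only rule and speaks of follow-up, which only enrolled patients have. The box is for patients without a study record, and its example justifies non-inclusion by ineligibility, not timing. This largely stands. A reader might infer that the two rules contradict each other generally, and the documents do not support that. What remains is that the operative sentence of the box is wider than its example, and the window makes the wider reading a routine situation.

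A reader might also infer that treatment drains necessarily enter the primary outcome, the "rate of routine prophylactic drain insertion in colorectal surgery". That is not shown. Appendix A records the reason for the drain, urgency, perforation and contamination, and nothing says that every drain counts as prophylactic. Emergency and contaminated cases are eligible without the box. The definition of the numerator may stand in an analysis plan that is not shown. The limit of this defence is that no listed reason means treatment of an established leak or collection, so these cases would probably share a code with ordinary emergency resections or sit in free text.

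A reader might see a further conflict with Appendix C, which says of negative exploratory laparotomies that "they should not be recorded as complications". It does not add to the point. The Re-operation row serves to prevent a second entry, while the recorded field is the highest Clavien-Dindo grade with reference to Appendix C, so the specific rule governs.

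The box covers only patients still in hospital, so readmissions fall outside it. This also holds the numbers down.

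**Conclusion.** The point holds in a narrow form. For a same-admission return to theatre after an eligible operation done before the window, the box and the Re-operation row give opposite instructions, and no field lets the analyst find these patients reliably afterwards. The harm falls mainly on the collection rate and on the comparison of time to diagnosis between drained and undrained patients. The effect on the primary outcome is uncertain.

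The size rests wholly on assumed inputs: roughly 0.3% to 6.7% of the cohort, with about 2% in a middle case, and lower where a patient was already included from an earlier period. The rise of 0.1 to 4.3 points applies to a crude any-drain rate only, and only if the recorded reason is ignored. Even a small share of the cohort can matter for detection time, because these cases would concentrate among collections in drained patients.

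**What to change.** In Section 6, limit the box to patients whose earlier procedure was not an Appendix B operation. Add a sentence stating that a same-admission return to theatre for a complication of an eligible operation done before the window is not a new index case.

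Alternatively, enter such patients with a flag on the case report form and leave them out of the primary, collection-rate and time-to-diagnosis analyses.

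The cost is two sentences, or one sentence and one form field, and a slightly smaller cohort. The aneurysm example can stay as it is.

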However, currently, the routine use of prophylactic drains after colorectal surgery is still widespread (15). As part of our last EuroSurg study, IMAGINE (16), centres filled out a survey regarding their adherence to ERAS guidelines. Preliminary data has shown that 35% of participating centres routinely leave drains after colorectal surgery for most of their patients.

Reasons to justify drainage after colorectal surgery include: prevention of complicated intra-abdominal collections; early detection of haemorrhage, anastomotic leakage, or other complications, and reduction of the incidence of anastomotic leak and pelvic sepsis (17,18). On the other hand, the routine placement of prophylactic drains is also associated with adverse events. Drains have been shown to be associated with an increased production of serous fluid, which could lead to wound infections, promote adhesions and could even result in a higher risk of anastomotic leak (19,20). In addition, they could cause irritation and offer an inward track for contamination.

It is common opinion that early detection of intra-abdominal collections might prevent additional surgical or percutaneous procedures necessary during the postoperative period (21). However, there is no consensus on which type of drain should be used and for how long it should be left in situ.

The aim of this international multi-centre cohort study is to define the incidence of drain placement after colorectal surgery and to describe drain management practices.

Methods

1. Definition for intra-abdominal collections

Postoperative collection altering the normal postoperative course management and requiring antibiotics or radiological/endoscopic/surgical intervention.

2. Summary

“Mini-teams” of up to three collaborators (medical students and/or doctors) per data collection period will prospectively collect data over a continuous 14-day period at each participating centre. This will be on consecutive patients undergoing elective or emergency colorectal surgery, with follow-up to 30 postoperative days. All mini-teams should be supervised by one surgical consultant of reference per centre. Each participating centre will be required to fill out a survey regarding their local drain management practices.

3. Study Aims

- **Primary Aim:** To audit compliance to Enhanced Recovery After Surgery (ERAS) guidelines on avoiding routine placement of prophylactic drains in colorectal surgery.
- **Secondary Aims:**

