- Time (measured in whole days) until drain removal and drain output (quantity and contents) on day of removal. Daily output will be calculated adding up the volumes drained in the 24 hours prior to the morning ward round. Contents are defined as serous fluids (with or without blood staining), frank blood, purulent and faecal.
- Overall 30-day adverse event rate as defined by the Clavien-Dindo scale of postoperative complications (25) and length of stay (days).

- ▲ Day of surgery is defined as Post-operative Day (POD) 0. The day after surgery is therefore defined as POD 1 and day 10 after surgery as POD 10. ▲

8. Measuring drain output

Drain output (volume and contents) should be assessed daily until removal or for the first ten days after surgery (Day 0: day of surgery – Day 10).

Strategies to record drain output and day of drain removal

- Speaking to ward staff, including doctors and nurses
- Reviewing patient notes daily, particularly drain charts
- Participating in daily ward rounds and doctor reviews

Remember: recordings of drain output must correspond to the entire day (8am to 8am). It is advised that you collect data one day in retrospect to capture all relevant data.

9. Covariates

Data will be collected on audit standards, and confounding factors for risk of intra-abdominal postoperative complications to permit accurate risk adjustment of outcomes. Without appropriately adjusting for risk factors, it is likely that any findings would be biased and unable to be appropriately analysed on a national scale. Data will **not** be analysed at a surgeon-level or centre-level. A full list of required data fields is available in Appendix A, and on the REDCap database.

10. Follow-up

Patients will be followed for 30 days after surgery. All secondary outcome measures will be recorded if they occurred at any point from postoperative Day 0 (day of surgery) to Day 30.

No change to routine follow up should take place. Collaborators should be proactive in identifying follow up data, but this should be done within the limits of routine follow up.

Strategies for follow-up include:

- Regularly reviewing patient notes to identify in-hospital complications.
- Participating in daily ward rounds and doctor reviews.
- Reviewing clinic notes and clinic letters, if seen in clinic by 30 days.
- Checking electronic systems and handover lists for re-admissions.
- Checking for emergency department re-attendances.

11. Data Analysis & Sample Size

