Intraoperative complications	None / Vascular injury / Bowel injury (e.g. duodenum) / Injury to other organs or structures (e.g. ureter)
Abdominal drain(s) inserted at time of surgery	Yes / No
Reason for drain identified	
Not identified Excessive intraoperative blood loss (or concern regarding this). Excessive intraoperative fluid (not blood) collections (or concern regarding this). Contaminated or dirty surgery

	
Positive air leak test (the intra-operative air leak test is a common intraoperative test used to identify mechanically insufficient anastomosis)
 
Poor vascularisation of the anastomosis (determined visually or by ICG fluorescence) (or concern regarding this).
 
Other reason identified (please specify)

Number of drains	Number
Type of drain(s) used	
Open (open drains drain fluid on to a gauze pad or into a stoma bag e.g. Penrose) / Close (tubes draining into a bag or bottle, e.g. Jackson-pratt).
 
Active (drains maintained under suction) / Passive (drains that have no suction and work according to the differential pressure between body cavities and the exterior).
 
(see REDCap for pictures)

Drain location	
Subcutaneous drain
 
Intraabdominal drain – pelvis
 
Intraabdominal drain – peritoneal cavity
 
Intraabdominal drain – posterior to the anastomosis
 
Intraabdominal drain – anterior to the anastomosis
 
Intraabdominal drain – near the anastomosis (not in contact)

Daily postoperative data points (to be completed for each inserted drain)	Required data (definition / comment)
Day of surgery is defined as Post-operative Day (POD) 0. The day after surgery is therefore defined as POD 1 and day 10 after surgery as POD 10.	
Volume drained (Daily POD 1-10)	
Millilitres (recordings of drain output must correspond to the entire day, i.e. 8am to 8am).
 
It is recommended that you collect data one day in retrospect.

Contents of drain output (Daily POD 1-10)	
Serous fluid (with or without blood staining) / Frank blood / Purulent / Faecal
 
(see REDCap for pictures)

Drain-related data points	Required data (definition / comment)

Day of drain removal	Post-operative Day (POD)
Surgical site infection	Yes – Site of Drain(s) / Yes – Other incision / No As defined by US Centers for Disease Control and Prevention (CDC)

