Surgical site infection type	Yes - Superficial (skin or subcutaneous tissue) / Yes - Deep (fascial and muscle layers) / Yes - Organ/Space SSI (intrabdominal) / No .
Small bowel evisceration/herniation of omentum	Yes – Site of Drain(s) / Yes – Other incision / No Prolapse of small bowel and/or omentum through an incision.
Drain-related iatrogenic bowel perforation	Yes - Intraoperative / Yes – Postoperative (not during removal) / Yes – Postoperative (during removal) / No.
Drain-related skin irritation	Yes (reversible damage of the skin at the drain insertion site associated with rash, dry skin, itchiness, red discolouration and/or hives) / No
Other Drain-related complication	Please specify
Reason(s) for drain removal	
1. Clinical rationale:
 
a). Drain output satisfactory (Yes, No) - if yes: low volume, (haemo)serous fluid, other (please specify).
 
b). Drain-related complications.
 
c). Inadvertent/premature drain withdrawal.
 
d). Other (please specify)
 
2. Radiological confirmation of no significant ongoing collection (Yes - pre removal, Yes - post removal, No).

Post-operative blood transfusion	Yes / No
Day of blood transfusion	Post-operative Day (POD)
History of collection(s) requiring treatment within 30 days (either medical, surgical, endoscopic, radiological)	Yes / No
Day of collection(s) identification	Post-operative Day (POD)

Collection(s) identification method	
1. Clinical only
 
a). Symptoms. b). Change in drain output (if inserted at time of surgery).
 
2. Radiological
 
a). Imaging due to clinical suspicion b). Routine imaging as per hospital policy c). Incidental finding (imaging for other indication).

Collection(s) treatment	
Conservative management (none or antibiotic therapy) Percutaneous drainage Surgery

Total postoperative antibiotic duration	
Number of days (Total antibiotic duration including both intravenous and oral antimicrobial therapy for the treatment of the collection(s). Post-operative antimicrobial therapy started before the identification of the collection(s) should not be included.)

Outcome data points	Required data (definition / comment)
Anastomotic leak within 30 days	Yes - Radiological diagnosis / Yes - Surgical diagnosis / No
Day of anastomotic leak diagnosis	Post-operative Day (POD)
Length of hospital stay (days)	Days
30 day readmission	Yes / No

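### The collection outcomes are intra-abdominal, but the Appendix A field that feeds them records no anatomical site, so treated wound collections can be counted

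*Protocol*

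**What the plan says.** Protocol section 7 (Outcome Measures, part II) lists "Rate of intra-abdominal postoperative collections, defined as collections which alter the normal postoperative course" and "Time-to-diagnosis (days) of intra-abdominal postoperative collections". Both carry two qualifiers: intra-abdominal and postoperative.

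Methods section 1 gives the definition. Its heading says intra-abdominal, but its body reads "Postoperative collection altering the normal postoperative course management and requiring antibiotics or radiological/endoscopic/surgical intervention" and names no site.

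In Appendix A the entry that opens the collection block is "History of collection(s) requiring treatment within 30 days (either medical, surgical, endoscopic, radiological"), answered Yes or No. The items that follow are "Day of collection(s) identification", the identification method, the treatment and the antibiotic duration. None asks where the collection was. Section 9 describes Appendix A as the full list of required fields, also held on REDCap.

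The same appendix does record site elsewhere. Drain location includes "Subcutaneous drain" as well as several intra-abdominal positions, and surgical site infection is recorded both by incision and by depth.

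Section 10 says secondary outcomes are "recorded if they occurred at any point from postoperative Day 0 (day of surgery) to Day 30".

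**The concern.** The data field is wider than the outcome it is meant to supply. Read literally, an abscess, seroma or haematoma in the wound that was treated within 30 days earns a Yes. No analysis plan can undo this, because a site that was never collected cannot be analysed.

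Two of the study's secondary aims depend on this field: whether a drain is associated with earlier detection of collections, and how often complicated collections occur. Because a subcutaneous drain is a permitted entry, a wound collection noticed through one could be coded as found by a change in drain output, and so look like detection by an abdominal drain. There is also one day item for one or more collections. If a wound collection came before an intra-abdominal one in the same patient, the recorded day could belong to the wrong event.

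Validation may not expose the problem. Under section 14, validators independently re-collect key outcome fields by reference to Appendix A. A validator who reads the same wording can agree with a misclassified entry, and the accuracy target above 98% would still be met.

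**Working it through.** **Text comparison**

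| Place in protocol | Site stated? | Postoperative stated? |
|---|---|---|
| Section 7, rate and time to diagnosis | Yes | Yes |
| Section 1, heading | Yes | No |
| Section 1, body | No | Yes |
| Appendix A, collection Yes/No | No | No; a 30-day limit only |
| Appendix A, day of identification | No | Given as a postoperative day |
| Appendix A, method, treatment | No | No |
| Appendix A, antibiotic duration | No | Yes |
| Appendix A, infection type | Yes, by depth | Not linked to the collection or its day |

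A related inconsistency lies in the same block: the opening field is for collections that required treatment, yet one treatment option is "Conservative management (none or antibiotic therapy"), which allows for no treatment. The two should be reconciled.

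**Possible size (illustration)**

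The protocol gives no collection rate, so there is no figure to reproduce. Let p be the assumed true rate of intra-abdominal collections and w the assumed rate of treated wound collections among the other patients, all of them recorded.

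Recorded rate = p + (1 − p)w. Share outside the definition = 1 − p / recorded rate.

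With p = 5%:
- w = 1%: 0.05 + 0.95 × 0.01 = 5.95%; share outside 1 − 0.05/0.0595 = 16%
- w = 3%: 0.05 + 0.95 × 0.03 = 7.85%; share outside 36%
- w = 5%: 0.05 + 0.95 × 0.05 = 9.75%; share outside 49%

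In the anticipated sample of about 5000 these are roughly 48, 142 and 238 extra patients. Over the same range of w, the recorded rate runs from 4.0% to 7.9% if p = 3%, and from 10.9% to 14.5% if p = 10%.

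**Direction between patients with and without drains**

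- Equal w in both groups, p = 5% undrained and 3.5% drained (true ratio 0.70), w = 3%: (0.035 + 0.965 × 0.03) / 0.0785 = 0.06395 / 0.0785 = 0.81, which is nearer to 1.
- Unequal w, p = 5% in both groups (true ratio 1), w = 4% drained and 2% undrained: (0.05 + 0.95 × 0.04) / (0.05 + 0.95 × 0.02) = 0.088 / 0.069 = 1.28. With the two wound rates exchanged the ratio is 0.78.

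For time to diagnosis, assume a mean of 7 days for intra-abdominal and 9 days for wound collections in both groups, with p = 5%. The recorded mean is (0.05 × 7 + 0.95w × 9) / (0.05 + 0.95w): 7.55 days at w = 2% and 7.86 days at w = 4%. That is an apparent gap of 0.31 days with no true difference.

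All these rates, ratios and days are assumptions. They show range and direction only.

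**The case against.** The field is not a collector's only guidance. Section 1 is headed as a definition of intra-abdominal collections, section 7 repeats the restriction for both outcomes, and section 10 ties what is recorded to the secondary outcome measures. Appendix A is to be used with a case report form, and neither that form nor the REDCap screens are among the documents. This stands: the text shows that wound collections can enter, not that they do. A reader might infer that the recorded rate is necessarily inflated, but the documents do not establish that.

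A reader might also infer that the comparison is diluted towards no difference. That needs wound collections to be equally common with and without a drain. The study background says that drain-related fluid could lead to wound infections, and section 7 counts surgical site infection among drain-related complications. Equal rates are therefore not a safe premise, and the direction is open.

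The infection-type item does some repair. A collection in a patient whose only infection is superficial can be flagged in a sensitivity check. Sterile seromas and haematomas, and patients with more than one problem, stay unresolved. Wound infections opened at the bedside without antibiotics are grade I in Appendix C, so they do not clearly count as requiring treatment.

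Lastly, a reader might infer that collections which prompted an emergency operation would be entered on day 0, mostly in drained patients, and imitate early detection. The support is weak: the outcome is postoperative, the day is a postoperative day, and section 10 counts what occurred from Day 0. What is left is a small gap, since the field does not say that the collection must be identified after the operation.

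**Conclusion.** The mismatch is real and worth correcting. Section 7 confines two secondary outcomes to intra-abdominal postoperative collections, and the field that supplies them, with its linked items, holds no site. Treated wound or subcutaneous collections can be recorded as the outcome and can be only partly identified later.

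On the assumed 5% true rate and 1% to 5% wound rate, the recorded rate would be about 6.0% to 9.8%, with 16% to 49% of events outside the definition. This is the size if collectors follow the field literally; if they apply the section 7 restriction, it shrinks towards nothing. No direction of bias can be claimed for the drain comparison. The primary outcome, adherence on drain insertion, is untouched.

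**What to change.** Reword the Appendix A and REDCap field to: *Postoperative intra-abdominal or pelvic collection requiring treatment, POD 0–30: Yes / No*. Add the note: *do not enter wound or subcutaneous collections; record these under surgical site infection or complication grade*. Put the word intra-abdominal into the body of the section 1 definition as well as its heading.

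As a minor addition, state that the day recorded is the day a collection was first identified after the index operation, so that one that was the reason for surgery is not entered as a POD 0 diagnosis. A blanket exclusion of any collection known or found at the operation would go too far: a persistent or recurrent collection treated postoperatively can meet the section 1 definition.

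The cost is the wording of one field with its note, one clarification of the day item and one definition sentence. No new data source, procedure or change in patient care is needed. It has to be done before data collection, because the site cannot be recovered from the database afterwards.
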